6.5.2.4 Immunogenicity Assessment

Blood samples (5 mL each) will be taken into serum separator tubes at each time point as outlined in [Table 3](#). At Visits 1, 6, 8, 9, 10, 11, 12, 13 and 15, five (5) blood samples of 5 mL each (25 mL total volume) will be drawn. The blood samples will be taken pre-dose by direct venipuncture, and the exact times of blood sampling will be recorded in the CRF. Two of the samples will be used to determine the presence of ADA against insulin aspart using the approach outlined below. One sample will be used to determine the presence of NAb against insulin aspart for samples that are ADA positive. Two samples will be collected and stored in reserve for potential supplemental immunogenicity testing and/or characterization including titer assessment if needed. Samples collected pre-dose at the randomization visit (Visit 6) will be considered as baseline. Samples collected at screening and the supplemental samples collected at baseline may also be used for method development and validation. Sample handling, processing, and storage instructions will be detailed in a separate laboratory manual.

A conventional radioimmunoprecipitation assay (RIPA) will be employed for the assessment of ADA in clinical samples. In this assay, samples will undergo a pre-treatment step that includes acid dissociation to release any anti-insulin antibodies complexed with free drug, followed by charcoal adsorption of the free insulin analog. The treated samples will be incubated with a fixed amount of ^{125}I -MYL-1601D tracer under conditions specified for each tier:

Screening Assay (Tier 1):

- RIPA Assay buffer only

Confirmatory Assay (Tier 2):

- RIPA Assay buffer only
- RIPA Assay buffer with excess unlabelled MYL-1601D
- RIPA Assay buffer with excess unlabelled Human Insulin
- RIPA Assay buffer with excess unlabelled NovoLog

Titer assay (Tier 3)

- RIPA Assay buffer only (multiple serial dilutions of the sample)

Anti-drug antibody complex formation with the tracer is measured via gamma counter and expressed as a percentage of bound to total radioactivity (%B/T).

In keeping with the multi-tiered sample analysis recommendations for immunogenicity testing from published white papers ([Mire-Sluis AR et al, 2004](#); [Shankar G et al, 2008](#)), and

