2. Standard-of-care specifics includes assessment and documentation of the following - Training on self-management of diabetes, lifestyle modification measures (includes maintenance of appropriate body weight, following recommended physical activity, avoidance of smoking and following the recommended diet); and monitoring to prevent complications.
3. Serum pregnancy test for women of child bearing potential will be done during screening and randomization visits (V1 and V6). During subsequent visits urine pregnancy test will be done, any positive urine test needs to be confirmed with serum test. At the randomization visit, both urine and serum pregnancy tests will be done, subject can be enrolled only if the urine pregnancy test is negative until serum result is provided.
4. Non-severe hypoglycemic events (which are not consider as SAE) occurring after the EOT visit will not be recorded at the follow-up visit.
5. A routine urine dipstick test will be performed by the site. A microscopic urinalysis will be performed by the central lab if the dipstick test result is abnormal and the Investigator deems it clinically significant and requests further evaluation.
6. Rescue criterion is evaluated on V12/Week 16 based on HbA1c measurement at V11/Week 12. Sites are required to receive the V11/Week 12 results prior to V12/Week 16 subject visit to enable Investigator to take decision on future steps.
7. The 7-point SMBG profile recorded via glucometer and recorded by the subject in the diary, measurement will be performed by the subject at home on 3 days (of which 2 days are consecutive) in the week before the visit.
8. Prior to randomization, Investigator is required to re-confirm subject eligibility to the study based on the data collected during the screening period, including the labs values recorded during screening.
9. Immunogenicity samples: At Visits 1, 6, 8, 9, 10, 11, 12, 13 and 15. At each visit, five blood samples of 5 mL each (25 ml per visit) will be drawn for ADA and NAb.
10. In case the subject discontinues treatment early, the site should explain the importance of data collection and make every effort to retain the subject, perform the remaining visits, off study treatment, per the Schedule of Study Assessments, up to the completion of Week 28/Follow-up call. BMI is calculated at screening visit, randomization visit, week 12 and week 24.

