7 STATISTICAL CONSIDERATIONS AND ANALYSIS

7.1 Derived Variables

The below table provides the list of derived variables for Demographic and baseline characteristics, various duration derivations, drug compliance, baseline derivations and other important derivations applicable for this study.

Table 3.

Variables	Formula
Demographic and Baseline characteristics	
Body mass index (BMI) (kg/m ²)	weight (kg) / [height (m)] ²
Derivation of Duration	
Study day at any visit	Date of interest – date of first dose of study drug. One day is added if this difference is ≥ 0
Extent of Exposure (Days)	Date of last randomized study medication intake – Date of first randomized study medication intake + 1
Extent of Exposure (Weeks)	Extent of exposure (days)/7
Baseline Derivations	
Baseline	Last non-missing value collected prior to the first dose of study medication in treatment period.
Change from baseline	Post baseline value – Baseline
SMBG Derivations	
SMBG excursion	Post-meal blood glucose – Pre-meal blood glucose
Mean SMBG	All BG/7 and average over 3 days
Mean excursion	All excursion values average over 3 days

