If baseline value is missing, the missing baseline value will be imputed with multiple imputations (6 imputations) using no missing baseline values from same treatment group. After imputation, the TEAR criteria will then be applied to each imputed dataset to obtain if a subject is TEAR positive or negative, and the treatment difference and 90% confidence interval will be estimated using Wald confidence limit method. The result will be combined over all imputations by SAS PROC MIANALYZE.

Tipping-point analysis will be performed via the method proposed by Liublinska and Rubin (2014). This will include a graphic display to indicate the tipping point analysis for the TEAR status binary outcome. A graphic display (heating map) is used to indicate the tipping point analysis results with missing values as TEAR positive. The treatment differences are presented as values in the heat map. The graph will be displayed to show the sensitivity ranging from missing favour testing treatment to missing favour reference treatment.

For tipping-point analysis, the number of subjects with missing data include 1) subjects who are missing all post-baseline ADA data, 2) subjects with partially missing ADA data whose TEAR status cannot be determined as positive or negative, and 3) subjects who are missing ADA data at baseline. If a subject with partially missing ADA data already meets the TEAR criteria, the subject is not considered as a subject with missing data.

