For continuous-valued ADA titer, missing values prior to the last observed visit will be filled in with MCMC imputation to make the dataset monotone. Missing values after discontinuation will be imputed by regression imputation of the monotone missing dataset. If there are at least 6 retrieved dropouts in each treatment arm, then a pattern mixture model estimated from the retrieved values will be used for regression imputation of missing values. Otherwise, the complete case missing values method will be used. Missing values for the binary response variable will be imputed using a logistic regression multiple imputation model. A monotone missingness pattern will be created by taking a random draw from the binomial distribution with the same probability as the observed responses from the same treatment group at the same visit.

Pattern mixture models will be fit separately for ADA binary response and for ADA titer. Binary response will be imputed using a logistic regression imputation model, while ADA titer will use a continuous-valued regression. Independent variables in the regression will include the values at all prior visits. Each imputation will be repeated 30 times with a seed of 40872021 for ADA binary response and a seed of 41671703 for ADA titer. Code for the multiple imputation analyses is presented in Appendix 10.1.

If baseline value is missing, the missing baseline value will be imputed with six imputations based on binomial distribution using probability of no missing baseline values from same treatment group.

After imputation, the dataset containing the imputed visitwise TEAR positive or negative status binary response and the dataset containing the imputed ADA titer values will be merged by subject, visit, and imputation number. The Week 24 values will then be used to assign the status of TEAR positive or negative, as follows:

If the subject was ADA negative at baseline, then this subject will be considered TEAR positive if any post-baseline observed or imputed value was ADA positive; otherwise, the subject will be considered TEAR negative. The imputed titer values will not be considered in subjects who are ADA negative at baseline.

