10.1 Multiple imputation

Multiple imputation will be applied to fill in missing values for ADA binary response and for ADA titer.

For binary ADA response, if baseline ADA value is missing, the missing baseline value will be imputed (6 imputations) based on binomial distribution using probability of no missing baseline values from the same treatment group. After imputations, for subjects with negative baseline ADA (Section 10.1.1) missing post-baseline binary response (positive or negative) will be imputed using logistic regression multiple imputation. For subjects who are ADA positive at baseline (Section 10.1.2), missing post-baseline ADA continuous titer values will be imputed with same treatment group non-missing subjects using continuous MI model.

The steps are summarised below:

Section 10.1.1 describes the methodology for imputation of binary response, while Section 10.1.2 covers the imputation of continuous ADA titer, and Section 10.1.3 puts them together.

10.1.1 Multiple imputation for binary ADA response if baseline ADA is negative.

For purposes of these specifications, let $RESP_x$ represent the binary value (0 or 1) at Visit x , where x takes the values 0 (for Baseline) or 8–15. The seed that will be used in the multiple imputation of ADA binary response will be 40872021.

Missing values will be obtained from logistic regression imputation on the observed values of binary response. A fully conditional specification (FCS) method will be used to impute values from a non-monotone missing data pattern.

There are 3 steps to this process:

1. Create a dataset with one record per subject, containing all values of $RESP$ for all weeks (Baseline and Weeks 2–24 on one record); that is, each record would contain variables for $RESP_0$ and $RESP_8$ – $RESP_{15}$. The subject-level $RETRIEVED$ variable described in Section 8.7.2.1 can also be generated at this time for subjects who discontinued treatment, based on whether values after treatment discontinuation

- were retrieved (set retrieved=1) or remain missing (set retrieved=0).
2. Fill in missing values to make a monotone missing data pattern, by drawing random TEAR values from the binomial distribution based on the TEAR frequencies for the given visit within treatment group.

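### A missing baseline ADA status is drawn from the arm's prevalence without the subject's own later ADA results, so a persistently positive subject can be counted as a treatment-emergent responder

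*SAP*

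**What the plan says.** SAP 8.7.2.1 states that, if the baseline is absent, "the missing baseline value will be imputed with six imputations based on binomial distribution using probability of no missing baseline values" in the subject's arm. I read the awkward wording as meaning the observed baseline values. Appendix 10.1 repeats the rule, "based on binomial distribution using probability of no missing baseline values from the same treatment group", and places it before the post-baseline imputation. SAP 7.2.1 does not name the binomial distribution, but it too relies only on other subjects' baselines: "using no missing baseline values from same treatment group".

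The status so obtained decides which TEAR rule applies (SAP 8.7.2.1). For a negative baseline, "this subject will be considered TEAR positive if any post-baseline observed or imputed value was ADA positive", and "The imputed titer values will not be considered in subjects who are ADA negative at baseline". For a positive baseline, TEAR requires a post-baseline titer at least four times the baseline titer.

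Baseline itself is defined in two ways. Protocol 6.5.2.4: "Samples collected pre-dose at the randomization visit (Visit 6) will be considered as baseline". SAP 7.1, Table 3: "Last non-missing value collected prior to the first dose of study medication in treatment period". The sampling schedule in SAP 3.3 reads "Immunogenicity samples: At Visits 1, 6, 8, 9, 10, 11, 12, 13 and 15", so each subject has one screening sample, one at randomization and seven afterwards.

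**The concern.** A baseline-negative subject needs one later positive to be a responder; a baseline-positive subject needs a 4-fold rise. The imputed baseline status therefore largely settles the endpoint for that subject. Up to seven later ADA results bear on what that status was, and the draw uses none of them. By contrast, SAP 8.7.2.1 imputes post-baseline values from a regression on all of the subject's prior visits.

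Take a subject positive at every later visit with a stable titer. Pre-existing antibody is the natural reading, yet the draw gives this subject the same chance of a negative baseline as anyone else in the arm. Once drawn negative, the subject is a treatment-induced responder, and the stable titers cannot correct it. The TEAR rate is the primary endpoint, and the NovoLog rate also sets the equivalence margin, so both could move.

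**Working it through.** **Inputs.** From the documents: 250 subjects per arm, a 90% confidence interval, and the margin table (SAP 5, Table 2). Not in the documents, so assumed over a range: baseline ADA prevalence q, the share of baselines missing, and the persistence, seroconversion and boosting rates.

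**The plan's own figure.** The margin is (z0.95 + z0.90) × √(2p(1 - p)/250), with the quantiles used in the SAP 10.2 code. At reference rates of 5, 10, 20, 30 and 50% it gives 5.70, 7.85, 10.47, 11.99 and 13.09 points, against 5.7, 7.9, 10.5, 12.0 and 13.1 in Table 2. The table reproduces.

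**One persistently positive subject, no 4-fold rise.** The correct TEAR status is negative. The probability of being counted positive is 1 - q: 80% at q = 0.2, 70% at 0.3, 50% at 0.5.

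**What the subject's own data would change.** Suppose, for illustration, that 90% of baseline positives and 10% of baseline negatives are positive at every later visit. Given an all-positive record, the probability of a negative baseline is 0.1(1 - q) / [0.1(1 - q) + 0.9q]:

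- q = 0.2: 0.08/0.26 = 31%, against 80% under the plan
- q = 0.3: 0.07/0.34 = 21%, against 70%
- q = 0.5: 0.05/0.50 = 10%, against 50%

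**Net error per missing baseline.** Let a be the chance that a baseline positive is positive again later, s the seroconversion rate among baseline negatives, and b the boosting rate among baseline positives. Assume that baselines are missing unrelated to ADA status, that a seroconverter drawn positive is not counted, and that a baseline positive drawn positive is counted at rate b.

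- True positive drawn negative, probability q(1 - q): excess a - b.
- True negative drawn positive, probability (1 - q)q: loss s.
- Net: q(1 - q)(a - s - b).

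| q | Upper bound (a = 1, s = b = 0) | a = 1, s = 0.3, b = 0.1 |
|---|---|---|
| 0.2 | 0.16 | 0.16 × 0.6 = 0.10 |
| 0.3 | 0.21 | 0.21 × 0.6 = 0.13 |
| 0.5 | 0.25 | 0.25 × 0.6 = 0.15 |

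**Effect on an arm's TEAR rate.** At the largest bound, 0.25 per missing baseline, 1, 2 or 5% missing adds 0.25, 0.5 or 1.25 points. As an extreme case, if every subject with a missing baseline were persistently positive and q = 0.3, the additions are 0.7, 1.4 and 3.5 points. For scale, the 90% half-width, 1.645 × √(2p(1 - p)/250), is 4.4 points at a 10% rate and 7.4 at 50%.

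**Effect on the margin.** With 5% of baselines missing and the 0.25 bound, a 10% reference rate becomes 11.25% and the margin goes from 7.85 to 8.27 points. From 20% it goes from 10.47 to 10.71; from 30%, from 11.99 to 12.13; at 50% it is essentially unchanged (13.09 to 13.08).

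**The case against.** The strongest reply concerns the screening sample. A reader might infer that the plan discards a measured Visit 1 result in favor of a random draw. The documents do not establish that. Under SAP Table 3 a non-missing Visit 1 result is the baseline, so the draw would apply only when Visits 1 and 6 are both missing. Only the protocol's Visit 6 definition would set the screening result aside, and the SAP does not say which governs the imputation. Nor is Visit 1 a perfect substitute. It precedes the 4-week NovoLog run-in, which some subjects enter from Humalog, so antibody arising in run-in would look treatment-emergent against it. Protocol 6.5.2.4 also allows screening samples to be used for method development and validation. All of this stands. It narrows the point to the draw itself and leaves two definitions to reconcile.

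Second, q(1 - q) is a ceiling. It requires no seroconversion and no boosting, whereas Table 2 plans for TEAR rates of 5 to 60%. This stands too. The net error is upward only while a exceeds s + b.

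Third, the same rule applies in both arms, so similar missingness largely cancels in the difference. The tipping-point analysis counts missing-baseline subjects among those with missing TEAR status, and an analysis without imputation is planned. These are fair but partial checks, since the primary decision still uses the draw.

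Two further inferences are tempting. One is that the six baseline draws cannot be matched to the 30 later imputations. The text does not explain the match, but the Section 10 flow chart is not visible in the copy reviewed and may do so. The other is that a subject drawn positive has no baseline titer to work with. The code in SAP 10.1.2 includes the baseline titer in its MCMC step, so it could be filled from later titers. Status would then ignore later data while titer used them, but whether this is intended cannot be judged from the text.

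**Conclusion.** The point holds in this form: as written, the draw ignores the subject's own post-baseline ADA status and titers. It misclassifies a persistently positive subject with no 4-fold rise in a share 1 - q of draws, and it can also remove TEAR status from a true seroconverter. The net error is at most 0.16, 0.21 or 0.25 cases per missing baseline at assumed prevalences of 20, 30 or 50%, and about 0.10, 0.13 or 0.15 at the assumed seroconversion and boosting rates.

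This is a minor defect. If few baselines are missing and both arms are affected alike, the arm difference barely moves, and the margin widens slightly at NovoLog rates below 50%. The documents do not support a claim that the equivalence conclusion is at risk, and they give no count of missing baselines from which to argue it. The case for acting is that the rule is avoidably wrong for identifiable subjects in the primary analysis and is cheap to replace.

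**What to change.** 1. Replace the marginal draw in SAP 7.2.1, 8.7.2.1 and 10.1 with joint imputation of missing baseline status and titer, from a model that includes the subject's observed post-baseline ADA status and titers.
2. Make one baseline draw for each of the 30 primary-analysis imputations, unless the Section 10 flow chart already sets out how the six draws combine with the 30.
3. Reconcile Protocol 6.5.2.4 with SAP Table 3. State whether a valid Visit 1 result serves as the ADA baseline when Visit 6 is missing, or instead enters the imputation model as a predictor. Note in the text that Visit 1 precedes the NovoLog run-in.
4. Report the number of missing ADA baselines by arm, so that the influence of the rule can be seen.

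The cost is SAP wording, a little more programming, and possibly the assay of a few stored screening samples, if they remain available and have not already been tested.

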7.1 Sample Size Determination

Approximately 500 subjects with type 1 diabetes will participate in this trial. The sample size estimation is based on primary objective - to demonstrate that immunogenicity as assessed by TEAR rate with MYL-1601D is equivalent to that of NovoLog® during 24-week treatment. The 80% power will be achieved with 250 subjects per treatment arm to demonstrate that 90% confidence interval of treatment difference (MYL-1601D minus NovoLog®) is within prespecified \pm margin (Table 5). (Chow SC et al, 2002; Chow S-C et al, 2003). The pre-specified equivalent margin is dependent on the final rate of NovoLog® TEAR rate. No replacement of subject will be performed if subject discontinued prematurely from the study. An attrition rate is not considered; for the analysis an imputation of missing values will be done and no patient will be excluded from the primary analysis.

Table 5: Margins and 95% CIs with different reference TEAR event rates in 500 subjects

Event Rate for Reference Product	Estimated 95% CI for the Event Rate (n=250)	Margin	Type I error 2 one-sided alpha	Power	Total N
5%	(2%,8%)	5.7%	0.05	80%	500
10%	(6%,14%)	7.9%	0.05	80%	500
15%	(11%,19%)	9.3%	0.05	80%	500
20%	(15%,25%)	10.5%	0.05	80%	500
25%	(20%,30%)	11.3%	0.05	80%	500
30%	(24%,36%)	12.0%	0.05	80%	500
35%	(29%,41%)	12.5%	0.05	80%	500
40%	(34%,46%)	12.8%	0.05	80%	500
45%	(39%,51%)	13.0%	0.05	80%	500
50%	(44%,56%)	13.1%	0.05	80%	500
55%	(49%,61%)	13.0%	0.05	80%	500
60%	(54%,66%)	12.8%	0.05	80%	500

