5 SAMPLE SIZE AND POWER

Approximately 500 subjects with type 1 diabetes will participate in this trial. The sample size estimation is based on primary objective - to demonstrate that immunogenicity as assessed by TEAR rate with MYL-1601D is equivalent to that of NovoLog® during 24-week treatment. The 80% power will be achieved with 250 subjects per treatment arm to demonstrate that 90% confidence interval of treatment difference (MYL-1601D minus NovoLog®) is within prespecified \pm margin (Table 2 of the SAP) (Chow SC et al, 2002; Chow S-C et al 2003). The pre-specified equivalent margin is dependent on the final rate of NovoLog® TEAR rate. No replacement of subject will be performed if subject discontinued prematurely from the study.

Table 2: Margins and 95% CIs with different reference TEAR event rates in 500 subjects

Event Rate for Reference Product	Estimated 95% CI for the Event Rate (n=250)	Margin	Type I error 2 one-sided alpha	Power	Total N
5%	(2%,8%)	5.7%	0.05	80%	500
10%	(6%,14%)	7.9%	0.05	80%	500
15%	(11%,19%)	9.3%	0.05	80%	500
20%	(15%,25%)	10.5%	0.05	80%	500
25%	(20%,30%)	11.3%	0.05	80%	500
30%	(24%,36%)	12.0%	0.05	80%	500
35%	(29%,41%)	12.5%	0.05	80%	500
40%	(34%,46%)	12.8%	0.05	80%	500
45%	(39%,51%)	13.0%	0.05	80%	500
50%	(44%,56%)	13.1%	0.05	80%	500
55%	(49%,61%)	13.0%	0.05	80%	500
60%	(54%,66%)	12.8%	0.05	80%	500

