6.2 ITT analysis set

The ITT analysis set includes all randomized subjects without being in the site with GCP violation (including subjects who receive incorrect treatment, do not complete the study or do not comply with the protocol or used prohibited medication, randomized but do not take any study drug). The subjects who are in the site with GCP violation will be excluded from ITT analysis set.

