8.7.1 Analysis methods

Definition of Primary Endpoints

The TEAR rate during 24-week treatment period is the primary endpoint for this study. TEAR is defined as either one of the following:

- 1) Subjects who are ADA negative at baseline and become positive at any timepoint post baseline.
- 2) Subjects who are ADA positive at baseline and demonstrate 4-fold increase in titer values at any timepoint post baseline visit.

Although differences in TEAR rate is the primary endpoint for the study from a statistical perspective, given that immunogenicity is not a standard endpoint in clinical trials, this difference, even if significant, will not be assessed in isolation but will be part of totality of evidence including changes in HbA1c, FBG, insulin dose, neutralizing antibodies and injection site reactions to ensure that changes in TEAR rate, if any, are clinically correlated and meaningful.

Statistical Methodology for Primary Endpoint

The 90% confidence interval of the treatment difference (MYL-1601D minus NovoLog®) in the TEAR rate will be established using the Wald confidence limit method with multiple imputation (Section 8.7.2.1). The MYL-1601D TEAR rate will be declared equivalent to that of NovoLog® during the 24-week treatment period if the 90% confidence interval of the treatment difference in TEAR rate is within the pre-specified margin as displayed in Table 2 of the study SAP, as suggested by Chow et al. (2002; 2003). For specific reference drug rate-based margin calculation, please refer to the SAS example code in Section 10 (Appendices – SAS Example Codes).

The primary analysis will be based on the ITT population. In addition, all post-discontinuation and rescue data will be included in the analysis.

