If the subject was ADA positive at baseline, then the imputed titer values will be used. The subject will be considered TEAR positive if the ADA titer at any post-baseline visit was $\geq 4\times$ the baseline titer. If none of the post-baseline titer values reached 4 times the baseline titer, then the subject will be classified as TEAR negative.

For each imputation, the proportion of responders, along with standard errors, will be estimated for each treatment group, and the estimate and standard error of the risk difference will be computed. These values will be combined across imputations using PROC MIANALYZE. Subsequently, the 90% confidence interval for the risk difference will be computed using the Wald confidence limit method.

An equivalence margin will be established as a function of the TEAR rate among the Novolog subjects. Under the null hypothesis of equivalence (i.e., $H_0: p_M = p_N$), the margin can be obtained as a function of the TEAR rate in the Novolog group using the following expression (Chow S-C et al., 2003, p. 91).

$$\delta = (z_\alpha + z_\beta) \sqrt{\frac{2p_N(1 - p_N)}{n_N}}$$

Selected values for δ are provided in Table 2 of Section 5 above. If the margin falls within the 90% confidence interval for the risk difference, then equivalence of MYL1601-D and Novolog will be declared.

These steps can be executed using code similar to the following:

```
proc freq data=simdata ;
title "90% Wald confidence interval";
by _imputation_;
ods output riskdiffcol2=rdiff1;
table group*resp / riskdiff (CL=WALD column=2) alpha=0.1;
weight count;
run;

data rdiff1; set rdiff1;
keep _imputation_ row risk ase lowercl uppercl;
if row='Difference';
run;

proc mianalyze data=rdiff1;
modeleffects risk;
stderr ase;
ods output ParameterEstimates=mirisk1;
run;

ods listing;
data parms1;
set mirisk1;
lowercl = estimate - (1.645*stderr);
uppercl = estimate + (1.645*stderr) ;
run;
proc print data=parms1;
var estimate stderr lowercl uppercl;
run;
```

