8.7.2.2 Secondary/Sensitivity analyses of the primary efficacy endpoint

Several sensitivity analyses will be conducted on the primary efficacy analysis:

- 1) The primary efficacy analysis will be repeated using observed data without imputation. This analysis will be conducted on both the ITT and the PP populations.
- 2) Subjects in the MYL-1601D group who are missing ADA values, and thus a TEAR assessment, will have their TEAR status at Week 24 imputed as positive. No imputation will be done for missing values in the NovoLog® group.
- 3) A tipping point analysis will be implemented following Liublinska and Rubin (2014). See below.

The ADA TEAR rate for each treatment group, and the difference between treatments, for

subjects who are missing data during the treatment period will be summarized for all sensitivity analyses.

The number and percent of subjects with TEAR will be summarized by treatment for each study visit during the treatment period by using similar TEAR definition: ADA negative at baseline become positive at specific visit, and ADA positive at baseline and become 4-fold increase in titer at specific visit.

A by-subject listing will be provided for observed and derived variables.

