10.2 Tipping Point Analysis

The tipping point analysis will create a type of figure called a heat map. It will not impute data at the subject level, but rather will be based on the observed total counts of TEAR status and number of missing values per group.

The steps are summarised below:

For purposes of the code below, set

```
Nm = Total # of subjects randomized to MYL-1601D group
Nn = Total # of subjects randomized to Novolog group
Mm = # of subjects missing TEAR status in MYL-1601D
group
Mn = # of subjects missing TEAR status in Novolog group
TEARm = # of subjects in MYL-1601D group who are TEAR
positive
TEARn = # of subjects in Novolog group who are TEAR
positive
```

Then run code similar to the following. The code below assumes that the above variables have been created as global variables.

```
%macro heat;

data heatmap;
do i = 0 to &mn;
  do j = 0 to &mm;
    y = &tearn + i;
    x = &tearm + j;
    pn = y/&nn;
    pm = x/&nm;
    riskdiff = pm - pn;
    margin = (quantile('NORMAL',0.95) +
    quantile('NORMAL',0.90))*
    sqrt(2*pn*(1-pn)/&nn);
    output;
  end;
end;
run;

%do i = 0 %to &mn;
  %do j = 0 %to &mm;

    data imputed;
    length group $8;
    group="NOVOLOG";
    status=1;
    count=%eval(&tearn+&i);
    output;
    status=0;
    count=%eval(&nn - (&tearn+&i));
    output;
```

```

group="MYL-1601D";
status=1;
count=%eval(&tearm+&j);
output;
status=0;
count=%eval(&nm - (&tearm+&j));
output;
run;

ods exclude all;
proc freq data=imputed;
table group * status / riskdiff (cl=WALD column=2)
alpha=0.1;
weight count;
ods output riskdiffcol2=rdiff1;
run;
ods exclude none;
data ci;
set rdiff1 (where=(row="Difference"));
y = &tearn + &i;
x = &tearm + &j;
run;

data heatmap;
merge heatmap
ci (keep=x y risk ase lowercl uppercl)
;
by x y;
length color $8 digits $16 a1-a6 asterisk $1;
if -0.0000001 <riskdiff < 0.0000001 then do;
red=255;
green=255;
blue=255;
end;
else if riskdiff > 0 then do;
if riskdiff >= 0.16 then do;
red = round(484 - (1435*riskdiff));
green = 0;
blue = 0;
end;
else do;
red = 254;
green = round(255/(1+exp(-32.96*(0.1149-
abs(riskdiff)))));
blue = round(255/(1+exp(-21.58*(0.0793-
abs(riskdiff)))));

```

```

        end;
    else if . < riskdiff < 0 then do;
        red = round(255/ (1+exp(-18.51*(0.1108-
abs(riskdiff)))));
        green = round(255/ (1+exp(-27.85*(0.1699-
abs(riskdiff)))));
        blue = round(255/ (1+exp(-20.10*(0.1024-
abs(riskdiff)))));
    end;

    digits = "0123456789ABCDEF";

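### The one-sided 0.05 in the margin tables is nominal: with the margin set from the observed NovoLog rate, the upper-bound error is about 8.8% at a 5% reference rate and 6.0% at 25%, and neither document says so

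*SAP*

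**What the plan says.** Protocol 7.1 and SAP 5 print the same table of margins for reference rates from 5% to 60%. Each row shows 0.05 under "Type I error 2 one-sided alpha", 80% power and 500 subjects. Protocol 7.1 adds: "The pre-specified equivalent margin is dependent on the final rate of NovoLog® TEAR rate". SAP 8.7.2.1 repeats this ("An equivalence margin will be established as a function of the TEAR rate among the Novolog subjects") and gives delta = (z_alpha + z_beta) × sqrt(2 pN(1 − pN)/nN).

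SAP 8.7.1 points to two routes to the margin. One is the table: the interval must lie "within the pre-specified margin as displayed in Table 2 of the study SAP". The other is the code: "For specific reference drug rate-based margin calculation, please refer to the SAS example code in Section 10". The code in SAP 10.2 uses the observed NovoLog count divided by the arm size, in the term "sqrt(2*pn*(1-pn)/&nn".

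Equivalence is declared when the 90% Wald interval for the difference lies inside (−delta, delta), according to SAP 8.7.1 and the hypothesis statement in 8.7.2.1. Neither document reports the error this rule attains.

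**The concern.** A fixed margin and a 90% interval give two one-sided tests at about 5% each. Here the margin is itself an estimate, drawn from the same NovoLog subjects as the difference. Its sampling error is missing from the standard error, and below 50% it pushes in the same direction as the error in the difference. A reader will take the 0.05 as the chance of declaring equivalence when the true MYL-1601D rate sits at the margin. At low reference rates that chance is higher, and on the side that the primary objective guards against: more antibody response on the test product. Protocol 2.2 says no TEAR rate is available from the innovator's studies and no expected rate is given, so the low rows cannot be ruled out.

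**Working it through.** **Inputs.** One-sided alpha 0.05, 80% power and 250 per arm (SAP 5); a 1:1 ratio (Protocol 4.1); Wald interval with multiplier 1.645 (SAP 8.7.2.1); margin constant z_0.95 + z_0.90 = 2.926 (code in SAP 10.2).

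**Reproducing the table.** delta = 2.926 × sqrt(2p(1 − p)/250) gives 5.70, 7.85, 9.35, 10.47, 11.33 and 11.99% at p = 5, 10, 15, 20, 25 and 30%, and 13.09% at 50%. The printed margins are 5.7, 7.9, 9.3, 10.5, 11.3, 12.0 and 13.1%. Using z_0.80 instead of z_0.90 gives 4.85% at p = 5%, which does not match. So the table was built with nominal alpha 0.05 and z_0.90.

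**Attained error.** Set pM = pN + delta(pN), the upper boundary of the null. Enumerate both binomials exactly, compute delta from the observed NovoLog rate in each outcome, and add up the probability that the 90% Wald interval lies inside ±delta.

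| True NovoLog rate | Margin from observed rate | Margin fixed at true value |
|---|---|---|
| 5% | 8.75% | 5.5% |
| 10% | 7.50% | 5.2% |
| 15% | 6.78% | 5.1% |
| 20% | 6.38% | 5.0% |
| 25% | 6.02% | 5.0% |
| 30% | 5.83% | 5.0% |
| 50% | 4.9% | 4.9% |

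The fixed-margin column shows that at 5% about 0.5 point of the excess is ordinary Wald error. The remaining 3.3 points or so come from estimating the margin.

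**Analytic check.** The upper bound is tested through T = pM − pN − delta(pN). Its variance is pM(1 − pM)/nM + (1 + delta′)² pN(1 − pN)/nN, with delta′ = 2.926 × sqrt(2/nN) × (1 − 2pN) / (2 × sqrt(pN(1 − pN))).

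- At pN = 5%: delta′ = 2.926 × 0.0894 × 0.90 / 0.436 = 0.540. The Wald SE is sqrt((0.0475 + 0.107 × 0.893)/250) = 0.0239. The SD of T is sqrt((0.107 × 0.893 + 1.540² × 0.0475)/250) = 0.0289. The error is Phi(−1.645 × 0.0239/0.0289) = 8.6%.
- At pN = 25%: delta′ = 0.151, the SE is 0.0409 and the SD is 0.0438, giving 6.2%.

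Both agree with the enumeration.

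**Lower bound.** Below 50% it is conservative: 1.4% at 10% and 3.0% at 20%. Above 50% the excess moves to this side but is small: 5.2% at 55% and 5.5% at 60%.

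**Sensitivity.** Arms of 225 to 250 give 8.8–8.9% at a 5% rate and 6.0–6.1% at 25%. Arm size matters because SAP 6.2 states "The subjects who are in the site with GCP violation will be excluded from ITT analysis set". If the margin is looked up in the table rather than computed, the nearest row gives 7.4% at a 5% rate and linear interpolation gives 8.5%. With 5% or 15% of data missing at random (assumed) and 30 imputations, simulation gives 8.6% at 5% and 6.0% at 25%.

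**The case against.** The strongest reply is that no printed figure is wrong. The 0.05 stands beside power and sample size as a design input, and it does generate the margins. Writing the attained values into that column would break it: at 5, 10 and 20%, with 80% power and 500 subjects, they would imply margins of 5.1, 7.3 and 10.0%. That part stands, which is why 0.05 should stay and only be labelled.

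The protocol also attributes the margin approach to the agency, warns that formal testing against a preset margin is difficult, and reads TEAR within the totality of evidence. This limits the consequence, but it neither states nor changes the attained error, and the choice of margin is not disputed here.

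The effect is also narrow. The excess is above about 1 point only in the 5–20% rows, four of twelve, and the trial may never fall there. That is true, but the plan cannot know it in advance.

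Finally, a supportive test will sometimes contradict a good result. With truly equal products, the primary rule passes and the supportive test fails in 10.4% of trials at a 5% rate (13.1% of those that pass), 6.7% at 10%, 3.5% at 20% and 2.0% at 30%. That cost is real and should be stated alongside the test.

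**Conclusion.** The point holds. The rule in SAP 8.7.2.1 does not have the one-sided 5% error that both tables show in every row. At the upper boundary the error is about 8.8% at a 5% NovoLog rate, 7.5% at 10%, 6.8% at 15%, 6.4% at 20% and 6.0% at 25%. The excess is under 1 point from 30% and absent at 50%.

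These figures assume 250 per arm, complete data, the formula margin with constant 2.926, and equivalence meaning that the interval lies inside the margin. The last sentence on the rule in SAP 8.7.2.1 words it the other way round and needs separate correction. Over 225–250 per arm, 5–15% missing data and either table-lookup method, the range is 7.4–8.9% at a 5% rate and 6.0–6.1% at 25%. The 7.4% is nearest-row lookup.

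**What to change.** Keep the Wald rule, the margin function and the 0.05 column.

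1. **Label and footnote.** In SAP Table 2, mark 0.05 as nominal and add a footnote along these lines: *attained one-sided error with 250 per arm, complete data and the margin computed from the observed NovoLog rate (constant z_0.95 + z_0.90 = 2.926) is about 8.8, 7.5, 6.8, 6.4 and 6.0% at reference rates of 5, 10, 15, 20 and 25%, and below 6% from 30% up (upper bound to 50%, lower bound above)*. Add the same to Protocol Table 5 at its next amendment. Until then the two tables do not conflict.

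2. **Supportive analysis.** Before unblinding, add an upper-bound analysis to SAP 8.7.2.2, where "Several sensitivity analyses will be conducted on the primary efficacy analysis". In each imputation compute T and its variance as in the working, with the actual arm sizes, and pool with PROC MIANALYZE. The criterion is met if T + 1.645 × SE < 0, and not met if any imputation has no NovoLog TEAR. By enumeration at 250 per arm this test has an upper-bound error of 4.7–5.1% for reference rates of 5–60%. No lower-bound version is needed, since the excess there is at most 0.5 point.

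3. **Standing of the result.** State that the primary rule alone decides equivalence, and that a discordant supportive result is reported as a caution within the totality of evidence.

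The cost is a footnote in each document, one paragraph and a few lines of code. The primary endpoint and its analysis do not change, so Protocol 7 does not require an amendment for this. The downsides are a stated error that looks worse at low rates and the discordance given above. With 15% missing data that discordance becomes 12.5, 7.9, 4.5 and 2.4% at 5, 10, 20 and 30%. If the primary margin is read from the nearest row, it is about 16.5% at a 5% rate, partly because two different margins are then being compared.
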